8. STUDY INTERVENTION DISCONTINUATION AND PARTICIPANT DISCONTINUATION/ WITHDRAWAL

8.1 Discontinuation of Study Intervention

Discontinuation for the study treatment does not mean discontinuation from the study and the remaining study procedures should be completed as per the Time and Event Schedule.

8.2 Participant Discontinuation/Withdrawal from the Study

The patients may withdraw from study treatment if they decide to do so, at any time and irrespective of the reason. In addition, the Investigator or the Sponsor has the right to withdraw the patient from the study and/or stop the study at any time. All efforts should be made to document the reason for discontinuation, and this should be documented in the electronic case report form (eCRF).

Other criteria for possible discontinuation are:

- Disease progression
- Unacceptable toxicity as judged by the Principal Investigator
- Adverse events which are dose-limiting toxicities
- Withdrawal of consent
- Subject is lost to follow-up
- Subject non-compliance
- Use of another non-protocol anti-cancer treatment
- Pregnancy
- Completed 24 months of study treatment

Withdrawn patients will be followed according to the study procedures as specified in this protocol.

The patients may withdraw from the study follow-up period, before study completion if they decide to do so, at any time and irrespective of the reason. The reason for withdrawal from the study treatment or study follow-up will be documented in the eCRF.

A patient who receives at least one study treatment and who discontinues from the trial for any reasons will not be replaced except for patients that withdraw for reasons other than toxicity during the safety run-in phase of the study.

8.3 Lost to Follow-Up

The Investigator should make every effort to re-contact the patient, to identify the reason why he/she failed to attend the visit, and to determine his/her health status, including at least his/her vital status. Attempts to contact

such patients must be documented in the patient's records (e.g. times and dates of attempted telephone contact, receipt for sending a registered letter). It is suggested that the Investigator attempts to contact the patient three times before considering the patient lost to follow up.

9. STUDY ASSESSMENTS AND PROCEDURES

Refer to the Time and Events Schedule [Table1](#) for an outline of the procedures required at each visit along with their associated windows. All patients must sign and date the most current approved ICF before any study specific procedures are performed. Procedures conducted as per standard of care or routine clinical management that are obtained before signing of the ICF may be utilized for screening/baseline purposes. All screening assessments may be performed within 28 days of Day 0 with the exception of screening labs (hematology and chemistry) which may be performed within 10 days of Day 0. Patients who discontinue will be asked to return to the clinic within 30 days of the last dose for a discontinuation visit. Generally, protocol waivers or exemptions will not be granted without discussion with the Sponsor.

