After consenting to participate in this clinical trial, participants will be screened for enrollment. A tissue sample is required for ASPH expression testing from either a fresh biopsy or archival tissue from a previous biopsy. Ideally, a pre-treatment tissue sample obtained after initiation of ongoing pembrolizumab, nivolumab or other CPI therapy and first dose of SNS-301 and pembrolizumab on this current clinical trial will be collected. Patients are requested to provide archival tissues from a prior biopsy or surgery that is treatment -naïve including prior 1) chemotherapy, radiation and 2) anti PD(L)-1 treatment-naïve, pending availability. The patient may start study treatment prior to receiving the ASPH expression results from the fresh biopsy or archival tissue from a previous biopsy. An on-treatment biopsy is required when medically feasible, after the third dose of the study treatment, treatment week 6. Additionally, up to two optional biopsies may be obtained in select cases at any time during the study, if medically feasible. For patients who progress as determined per RECIST1.1/iRECIST criteria, an optional biopsy will be obtained at the time of disease progression.

Patients will be enrolled into one of two cohorts depending on whether they are currently on a CPI or if they are naïve to CPI therapy as per the flow diagram below.

Checkpoint inhibitor = anti-PD1 and anti-PD-L1 agents

The following procedures will be performed:

1. For eligible patients, the study treatment of SNS-301 in addition to pembrolizumab will be initiated on Day 0 (First dose).
2. SNS-301 will be dosed approximately 1 hour after IV infusion of pembrolizumab for the first dose. Subsequent doses of SNS-301 and pembrolizumab can be dosed in any order. If pembrolizumab is discontinued by the Investigator prior to 24 months, treatment with SNS-301 vaccine therapy may continue for up to 24 months in patients without disease progression.
3. Tumor biopsies will be collected at the time of screening and at Week 6 (\pm 3 days) and at first evidence of radiographic or clinical disease progression if clinically deemed feasible. Patients who are unable to undergo biopsy sample collection during treatment but otherwise meet criteria listed in the protocol may continue to receive study treatment.

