Because this trial is treating patients with SNS-301 and pembrolizumab for the first time, there will be a waiting period of one week between enrollment of the first patient and the second patient.

Stopping Rules

The trial will be stopped if any adverse experience of any related death, grade 4 autoimmune toxicity or any grade 4 toxicity that is considered to have a causal relationship to study drug. Any related death, grade 4 autoimmune toxicity and any grade 4 toxicity that is considered to have a causal relationship to study drug will be submitted to regulatory agencies within the expedited safety reporting criteria.

Study treatment:

Study treatment include:

1. SNS-301 (1×10^{11} dose/1ml) ID injection using the 3M® hollow microstructured transdermal system (hMTS) device will be administered on Day 0, Week 3, Week 6 and Week 9 (± 3 days) then every 6 weeks (± 3 days) for 6 additional doses, and thereafter every 12 weeks (± 3 days) until confirmed disease progression, unacceptable toxicity, deemed intolerable by investigator or up to 24 months in patients without disease progression.
2. Pembrolizumab (200 mg dose) IV infusion over 30 minutes every 3 weeks or Pembrolizumab (400 mg dose) IV infusion over 30 minutes every 6 weeks will be administered until confirmed disease progression, unacceptable toxicity, deemed intolerable by investigator or up to 24 months in patients without disease progression. When possible, pembrolizumab should be given on the same schedule as SNS-301. The investigator should consult the sponsor if there are questions regarding aligning the study treatment schedule.

For the purpose of this protocol, study treatment is defined as SNS-301 added on to pembrolizumab, when given according to the US package insert. Refer to https://www.merck.com/product/usa/pi_circulars/k/keytruda/keytruda_pi.pdf for most recent package insert.

Statistical Methods:

Sample Size Justification:

Each cohort will enroll in two stages. Within each cohort, approximately 15 participants may be enrolled in Stage 1 and an additional approximately 15 participants may be enrolled in Stage 2, if expanded. The sample size for each cohort and stage is based on Simon's two-stage design for tests of one proportion.

Analysis Populations:

Safety Analysis Set:

The safety analysis will be based on the Safety Analysis Set, which comprises all patients who receive at least 1 dose of the study treatment or component of the study treatment.

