RECIST/iRECIST	X		Q6w from Day 0 until ~12 months, thereafter Q12w						
Hematology ^m	X	X ^f	X ^f	X ^f	X ^f	X ^f		X	
Serum Chemistry ⁿ	X	X ^f	X ^f	X ^f	X ^f	X ^f		X	
Coagulation Panel (aPTT, INR)	X								
Urinalysis ^o	X			X			X	X	
Pregnancy ^p	X	X	X	X	X	X		X	X
TSH, T3 and Free T4 ^q	X			X			X		
CPK	X							X	
HPV/EBV, if unknown	X								
PDL-1	X								
Blood samples for immunology assessments ^r		X	X	X	X	At week 12, then Q6 weeks until Week 36 and Q12w thereafter as well as at disease progression			
Tumor specimen	X			X		Up to 2 optional biopsies and at disease progression			
Adverse Events	X	X	X	X	X	X		X	X
Pembrolizumab ^u		X	X	X	X	X			

SNS-301 ^v		X	X	X	X	After week 9, Q6w for 6 more doses (week 45), thereafter Q12w until PD or 24 months if no PD		
Survival and new anti-cancer therapy follow-up ^w								X

Note: Assessments scheduled on the days of study treatment should be performed before the study treatment unless otherwise noted.

^a Written informed consent can be obtained up to 28 days prior to Day 0 and is required for performing any trial-specific tests or procedures. However, tumor tissue collection (archived or fresh) can exceed 28 days to ensure that sufficient time is available for obtaining the requested sample for trial purposes. Additionally, a pre-screening informed consent is available to obtain archived tumor tissue prior to the study's primary consent. Results of standard-of-care tests or examinations performed prior to obtaining informed consent and within 28 days prior to Day 0 may be used for screening assessments rather than repeating such tests. Screening labs (CBC and chemistry) may be used for Day 0 if they are within 10 days of Day 0.

^b Patients who discontinue early from study treatment (i.e., progression, adverse event, etc.), will be asked to return to the clinic within 30 days after the last dose for a treatment discontinuation visit.

^c Cancer history includes stage, date of diagnosis, and prior anti-tumor treatment. Previous progression data should be collected as well. Demographic information includes sex, age, and self-reported race/ethnicity. HPV, EBV, reproductive status and smoking/alcohol history should also be captured.

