7.4 Concomitant Therapy

All treatments including any prescription or over the counter medications taken by the patients seven days prior to screening and at any time during the study are regarded as concomitant treatments and must be documented in the appropriate section of the e-CRF. At subsequent visits, changes to current medications or medications used since the last documentation of medications will be recorded. Concomitant medications will be collected until 30 days after the last dose of study medication or until the start of a new anti-cancer treatment, whichever comes first.

7.4.1 *Allowed concomitant treatments*

The following concomitant treatments are permitted during this study:

- Supportive treatment will be given as medically indicated.
- Prophylactic antiemetic premedication including corticosteroids (low dose \leq 10 mg/day prednisone equivalent) and 5-hydroxytryptamine 3 antagonists.
- Supportive treatment with cannabis will be allowed, if medically indicated.

7.4.2 *Prohibited Medications or Treatments During Study*

Medications such as those listed below are not permitted in the course of the trial:

- Concurrent treatment with other investigational drugs
- Concurrent treatment with any other anticancer therapy including radiotherapy
- Traditional herbal medicines should not be administered because the ingredients of many herbal medicines are not fully studied, and their use may result in unanticipated drug-drug interactions that may cause or confound assessment of toxicity. However, if the investigator feels herbal medication is warranted the Sponsor should be consulted
- Initiation or increased dose of granulocyte colony-stimulating factors (e.g., granulocyte colony-stimulating factor, granulocyte/macrophage colony-stimulating factor, and/or pegfilgrastim) is strongly discouraged
- Patients are not allowed to receive immunostimulatory agents, including but not limited to IFN- α , IFN- γ , or IL-2, during the entire trial. These agents, in combination with study treatment, could potentially increase the risk for autoimmune conditions

7.4.3 *Rescue Medication*

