This is the first time the SNS-301 is given in addition to pembrolizumab to any patients. Although most immune-mediated adverse events observed with immunomodulatory agents have been mild and self-limiting, such events should be recognized early and treated promptly to avoid potential major complications. Discontinuation of SNS-301 or pembrolizumab may not have an immediate therapeutic effect due to the long half-life of the drug or longer drug effect, and there is no available antidote for the study treatment. In severe cases, immune-mediated toxicities may be acutely managed with topical corticosteroids, systemic corticosteroids, mycophenolate, or TNF- α inhibitors per investigator's discretion.

For instruction on how to handle pembrolizumab immune response adverse events refer to the pembrolizumab package insert.

Patients should receive appropriate medical intervention necessary to treat medical conditions as they arise.

7.5 *Dose Modification and/or Interruption*

For pembrolizumab, follow the package insert for dose modification instructions.

For SNS-301, there will be no dose reductions allowed for this study.

In case of non-DLT AE (grade 2 NCI-CTCAE V5.0 drug related AE), the dosing interval can be extended to up 42 days to allow the recovery from a related toxicity and the patient will resume at the same dose. If the patient experiences the same grade or higher toxicity and same grade requiring a dose-delay at the subsequent cycle, the patient should be discontinued from study treatment.

Should there be a clinically significant AE or SAE recorded relating to a patient receiving anticoagulants, such as clinically noted bleeding, administration of SNS-301 will be held until the AE/SAE returns to baseline. Should there be two individual events of SNS-301 interruption for the same patient, then SNS-301 will be discontinued after consultation with the Medical Monitor and Study Sponsor.

If a patient is unable to receive study treatment (e.g., due to COVID19) the dosing interval can be extended up to 42 days after consultation with the Sponsor and the rationale to be documented.

Treatment with SNS-301 may continue if pembrolizumab is discontinued by the Investigator, if prior to 24 months. If both study treatments are stopped for >42 days then the patient should be discontinued from study treatment and continue to the study follow up phase.

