9.2.14.5 Adverse Events

AEs will be collected from the time of informed consent until 30 days after the last dose of study treatment or until initiation of another anti-cancer therapy, whichever occurs first. SAEs and AESIs will be collected from the time of informed consent until 90 days after the last dose of study treatment or until initiation of anti-cancer therapy, whichever occurs first. See Section 9.3 for additional details on Adverse Events and Serious Adverse Events.

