Safety evaluations will be based on the incidence, severity, attribution and type of AEs, and changes in the patient's vital signs, and clinical laboratory results, analyzed using the safety analysis set.

Summarization of toxicity data will focus on incidence of treatment-emergent adverse events. Treatment-emergent adverse events are defined as any AE that occurs during or after administration of the first dose of treatment through 30 days after the last dose, any event that is considered study drug-related regardless of the start date of the event, or any event that is present at baseline but worsens in intensity. The incidence of serious adverse events, adverse events, drug-related adverse events, and adverse events leading to discontinuation or death will be presented in tabular form by system organ class and preferred term. Adverse events will be assessed for severity according to the NCI CTCAE, version 5.0.

A presentation of dose-limiting toxicities among patients in the safety run-in set will be presented.

Other safety evaluations including vital sign, laboratory and physical exam results will be presented over time.

10.4.4 *Other Analyses*

Antigen-specific cellular immune response assessed by but not limited to Interferon- γ secreting T lymphocytes will be summarized by visit. Immune related gene expression will be evaluated with pre- and post-treatment tissue biopsies. Cytokine and chemokine profiles will be summarized by visit.

Additional exploratory analyses may be performed, including evaluation of relationship between efficacy endpoints and immunology parameters.

10.4.4.1 *Pharmacodynamics*

Exploratory pharmacodynamic (PD) analysis will be performed using dose, vaccine-specific antibody response (geometric mean titer), antigen-specific T and B cell indices, and the relative expression of ASPH in each patient's tumor. The PD will be balanced and optimized to the degree of antigen-specific immune response and minimized for the production of regulatory immune processes.

10.5 *Interim Analyses*

For each cohort, the objective response rate will be assessed at the completion of stage 1 of the 2-stage design, after 15 patients complete the 12-week follow-up period or discontinue prior due to disease progression. See Section 10.2 for additional details.

10.5.1 *Safety Committee*

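### The discontinuation visit, non-serious AE and medication collection and the TEAE window all end 30 days after the last dose, which is before some discontinuations the protocol provides for, including every one under its >42-day rule

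*Protocol*

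**What the plan says.** Four limits share one clock, which starts at the last dose.

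- **Visit.** Protocol section 9: "Patients who discontinue will be asked to return to the clinic within 30 days of the last dose for a discontinuation visit". Footnote b of both schedules of events repeats it: patients who stop early "will be asked to return to the clinic within 30 days after the last dose for a treatment discontinuation visit".
- **Non-serious AEs.** Section 9.2.14.5: "AEs will be collected from the time of informed consent until 30 days after the last dose of study treatment or until initiation" (the sentence goes on to make a new cancer treatment the end point, if sooner). Synopsis procedures item 8, sections 9.3.1 and 9.3.13, footnote t and SAP 8.3 agree.
- **Medications.** Section 7.4: "Concomitant medications will be collected until 30 days after the last dose of study medication", or until new anti-cancer treatment if sooner. SAP 6.8 agrees.
- **TEAEs.** Section 10.4.3 and SAP 8.3 count events "during or after administration of the first dose of treatment through 30 days after the last dose". They add drug-related events whatever their start date, and baseline conditions that worsen.

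The dosing rules allow longer gaps. Section 7.5 lets a dosing interval stretch to 42 days and then says: "If both study treatments are stopped for >42 days then the patient should be discontinued from study treatment". SNS-301 is given three-weekly, then six-weekly, then twelve-weekly (7.1.2.1), and pembrolizumab three- or six-weekly (7.1.2.2). The synopsis prefers alignment ("When possible, pembrolizumab should be given on the same schedule as SNS-301") and allows SNS-301 alone: "If pembrolizumab is discontinued by the Investigator prior to 24 months, treatment with SNS-301 vaccine therapy may continue for up to 24 months".

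Serious AEs (SAEs) and AEs of special interest (AESIs) run to 90 days after the last dose (9.2.14.5). Section 9.3.5 collects SAEs to the end of the study.

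**The concern.** The clock runs from the last dose, but the decision to stop can come later. Where the time since the last dose already exceeds 30 days at that decision, the visit is out of window before it can be booked, and routine AE and medication collection has closed on paper.

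Safety and tolerability is a primary objective, measured by all AEs (4.2.1). The only AESIs are systemic administration site reactions (9.3.10), so the longer window does not reach non-serious laboratory or immune-mediated events. The clause admitting drug-related events at any time can act only on events that were recorded.

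Classification also comes to depend on outcome. On a 42-day interval, an event starting on day 35 is treatment-emergent if the next dose is given. If the patient stops, it is not, unless it is recorded and judged drug-related or is a worsened baseline event. That bears directly on the SAP 8.3 tables of TEAEs leading to discontinuation.

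**Working it through.** **Inputs.** 30-day limits: sections 7.4, 9, 9.2.14.5 and 10.4.3. Hold rules: 7.5. Dosing: 7.1.2 and Table 1. Alignment: footnote u of the six-weekly schedule. Scans: six-weekly to Week 54, then twelve-weekly (footnote l). Assumption: the last dose means the last dose of either drug, since 7.1.1 defines study treatment as both.

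**1. Reproduce the SNS-301 calendar.** Doses at Weeks 0, 3, 6 and 9, then six more six-weekly: 9 + 6 × 6 = Week 45, as footnote v of the three-weekly schedule states. Then Weeks 57, 69, 81 and 93. Footnote v of the six-weekly schedule and SAP 3.3 end this phase at Week 48, which needs a Week 12 start (12 + 36). Those passages must be reconciled, but 42- and 84-day gaps arise under either calendar.

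**2. The >42-day rule.** It is first met on day 43. 43 − 30 = 13 days past the limit, for every patient discontinued under it. A hold of 31 to 42 days that ends in stopping also misses the limit.

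**3. Planned gaps between doses of either drug, to Week 104.** Late days = sum of max(0, gap − 30): 12 for a 42-day gap, 54 for an 84-day gap.

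| Regimen | Longest gap | Gaps over 30 days | Late days / all days |
|---|---|---|---|
| Three-weekly pembrolizumab + SNS-301 | 21 days | 0 of 34 | 0/714 = 0% |
| Six-weekly, unaligned | 42 days, from Week 48 | 5 of 29 | 60/714 = 8.4% |
| Six-weekly, aligned (200 mg at Week 12 assumed) | 42 days, from Week 15 | 14 of 19 | 168/693 = 24.2% |
| SNS-301 alone | 42 days from Week 9, 84 from Week 45 | 10 of 13 | (6 × 12 + 4 × 54)/651 = 44.2% |

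For SNS-301 alone the share is 72/315 = 22.9% before Week 45 and 54/84 = 64.3% after it. On three-weekly dosing, both ±3-day windows together give 21 + 6 = 27 days, still inside 30. These are shares of calendar time, not of events or patients.

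**4. Where scans fall.**

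- Aligned six-weekly: doses at Weeks 15, 21, …, 51, 57, 63; scans at Weeks 18, 24, …, 54, 66. Each scan is 3 weeks (day 21) after a dose.
- SNS-301 alone: day 21 from the Week 12 scan to the Week 48 scan. Then Week 54 − 45 and 66 − 57 both give 9 weeks, day 63.
- Unaligned six-weekly after Week 48: the 42-day gaps run 48–54, 60–66 and so on, and scans at Weeks 54 and 66 fall at their end, day 42.

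On aligned dosing, and on SNS-301 alone before Week 45, the late discontinuations are therefore those for non-imaging reasons, such as toxicity found at the next visit (about day 42).

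**5. Does other text resolve it?** Table 1 marks AEs at the discontinuation and follow-up columns, but footnote t closes that row at day 30. Section 9.3.13 has any condition beginning after consent recorded as an AE with no end date, next to its own 30-day limit. Neither gives the visit another anchor. End-of-treatment imaging does have one: synopsis procedures item 7 times it from treatment discontinuation (±4 weeks).

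**The case against.** The strongest reply is that little is actually lost.

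- **Frequency.** A reader might infer that many discontinuations are affected. The documents give neither the regimen mix nor the timing of discontinuations. Three-weekly dosing has no planned gap over 30 days, and alignment is optional. This stands.
- **Progression.** A reader might infer that progression on aligned six-weekly dosing is found at about day 42. Scans fall about 21 days after a dose, although image review may wait until the next dosing visit. This stands.
- **Held doses.** A reader might infer that patients held for toxicity lose most. On three-weekly dosing the causative event usually starts before the held dose, about day 21, so it is captured even if discontinuation comes on day 43. This stands.
- **Tests.** A reader might infer that the discontinuation laboratory tests and the only post-baseline CPK (9.2.11) are lost. They are tied to the visit, not to day 30. SAP 3.3 sets no window for this visit, so late results can still be summarised. They are out of window rather than missing. This stands.
- **Contrary text.** SAEs are covered to 90 days or the end of study, and 9.3.13 and the Table 1 AE row suggest that recording continues. This narrows the exposure, but the passages contradict the 30-day statements rather than override them, and the TEAE definition still cuts at day 30.

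The reply does not remove the clash with the >42-day rule, which needs no assumption about regimen mix.

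**Conclusion.** The point holds in a limited form. Sections 7.5 and 9 cannot both be followed for a patient discontinued under the >42-day rule: the visit is at least 13 days out of window. Discontinuations can also fall after day 30 in these cases:

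- for non-imaging reasons on aligned six-weekly dosing or six-weekly SNS-301 alone, about day 42;
- on unaligned six-weekly dosing after Week 48, up to day 42;
- on SNS-301 alone after Week 45, with scans at about day 63 and the next dose at day 84.

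The share of planned treatment time beyond day 30 runs from 0% to 44.2% by regimen. The number of patients cannot be derived.

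The exposure is non-serious, non-AESI events that start after day 30 in patients who never resume, plus the medications used for them. Their treatment-emergent status then depends on whether dosing resumed. The documents do not support a claim that serious toxicity, laboratory or CPK data are lost. The result rests on reading the last dose as that of either drug, and on the Week 9 to Week 45 SNS-301 calendar.

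This should be corrected: it touches a primary objective, and the change is small.

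**What to change.** 1. Time the discontinuation visit from the decision to discontinue, for example within 30 days of it. This reconciles section 9 and footnote b with 7.5.
2. Collect AEs and concomitant medications to the later of 30 days after the last dose and that visit, still stopping at new anti-cancer therapy. Use the same end date in the TEAE definition.
3. End SAE and AESI collection at the later of 90 days after the last dose and that visit. Without this, an 84-day gap plus a visit 30 days after the decision takes non-serious collection to 84 + 30 = day 114, beyond the 90-day limit.
4. Reconcile 9.2.14.5, 9.3.5 and 9.3.13, which give different end points for SAE and AE recording.

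Places to amend: synopsis procedures item 8; protocol 7.4, 9, 9.2.14.5, 9.3.1, 9.3.13 and 10.4.3; footnotes b and t of both schedules; SAP 6.8, 8.3 and Appendix A.

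Cost: wording in both documents, slightly more AE data entry and slightly higher TEAE counts. The TEAE window would vary between patients, so the fixed 30-day count can be shown alongside. There is no new visit or test, and no dosing or stopping rule changes.
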